#### **Treatment Emergent Adverse Events**

- All deaths from start of treatment until 28 days after the final dose.
- All treatment related SAEs.
- All unrelated SAEs from treatment start until 28 days after final dose of treatment.

- All non-fatal AEs occurring after treatment start up until 28 days after final dose of treatment or until start of new anti-cancer treatment, whichever is first.
- Disease progression is not considered a treatment emergent adverse event unless the subject dies of disease prior to 28 days after discontinuation of treatment.
- Events that are continuations of baseline abnormalities are considered treatment emergent adverse events only if there is an increase in grade over baseline.

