## 8. HANDLING OF MISSING VALUES

### 8.1. Missing Dates

In compliance with Pfizer standards, if the day of the month is missing for any date used in a calculation, the 1st of the month will be used to replace the missing date unless the calculation results in a negative time duration (eg, date of onset cannot be prior to day one date). In this case, the date resulting in 0 time duration will be used. Pfizer standards are also used if both month and day are missing (Jan 1 unless negative time duration). This excludes the pharmacokinetic, ECG, and pharmacodynamic analyses, which will only use the actual date collected or if date not available deem the data missing.

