**Table 4: Time to Progression**

Situation	Date of Progression/Censoring 	Outcome
Inadequate baseline assessment	Start date (C1D1)	Censored
No on-study assessments	Start date (C1D1)	Censored
Alive, on treatment  and no Progression	Date of last objective tumor assessment	Censored
Progression Documented on or between scheduled tumor assessments prior to treatment discontinuation 	Date of first objective tumor assessment showing objective progression	Progressed (Event)
Treatment discontinuation for undocumented progression	Date of last objective tumor assessment prior to discontinuation 	Censored
Treatment discontinuation due to toxicity or other reason	Date of last objective tumor assessment prior to discontinuation 	Censored
New anticancer treatment <28 days after discontinuation of treatment without progression	Date of last objective tumor assessment prior to new anticancer treatment	Censored
Death prior to first planned tumor assessment	Start date (C1D1)	Censored
Death without objective progression prior to treatment discontinuation 	Date of last objective tumor assessment prior to death	Censored
Progression after 2 or more missed tumor assessments	Date of last objective tumor assessment prior to the event	Censored

1: For censoring date, if a tumor assessment takes place over a number of days (eg, superficial lesions one day, scans another), the last date is used as the assessment date.

2: or within 28 days of discontinuation of treatment.

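### Section 8.1 gives an incomplete start date of new anticancer therapy its earliest value, which can only shorten the treatment-emergent window that Section 7.2.6 sets for non-fatal AEs

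*SAP*

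**What the plan says.** SAP Section 8.1 applies "if the day of the month is missing for any date used in a calculation": the 1st "of the month will be used to replace the missing date unless the calculation results in a negative time duration". The illustration of the exception is "eg, date of onset cannot be prior to day one date", and the remedy is "In this case, the date resulting in 0 time duration will be used". With month and day both missing, 1 January is used under the same exception. The exemption is narrow: "This excludes the pharmacokinetic, ECG, and pharmacodynamic analyses". AE dates and dates of later therapy are therefore covered.

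SAP Section 7.2.6 (Treatment Emergent Adverse Events) counts non-fatal AEs from treatment start to 28 days after the final dose or "until start of new anti-cancer treatment, whichever is first". Separate bullets cover deaths and unrelated serious AEs (both to 28 days after the final dose) and related serious AEs (no end date). None of these is cut at new therapy. The same section defines treatment-related AEs as a subset of treatment-emergent AEs.

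SAP Section 9.2.3, which governs the AE tables, describes treatment-emergent AEs by onset or worsening after the first dose. It does not mention new therapy.

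**The concern.** An early imputed date is reasonable for an AE onset, which is the SAP's own illustration: with Day 1 as a floor, it tends to keep the event in the count. The start of new anticancer therapy does the opposite job, because it closes a window. The imputed start is never later than the true start except where the override moves it, and no rule requires it to fall after the last study dose. The error therefore runs one way, towards fewer treatment-emergent AEs and a drug that looks better tolerated.

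Non-fatal, non-serious AEs are at stake. One that drops out of the treatment-emergent set also drops out of the related set. Safety and tolerability stand in the primary objective of both parts (Section 2.4), and Section 5 expects 2 to 12 patients per dose. One patient is then between 1/12 = 8% and 1/2 = 50% of a dose group.

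**Working it through.** The SAP gives no figure on this point, so there is none to reproduce. The rules come from Sections 8.1 and 7.2.6. Gaps, treatment lengths and the distribution of dates are assumptions.

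**1. Worked example.** First dose 2 March, last dose 4 May, new therapy truly starts 27 May but is recorded as 'May'. The imputed start is 1 May. It is later than Day 1, so a check against Day 1 does not fire. The true window runs to 27 May, since 28 days after the last dose is 1 June. The imputed window closes on 1 May, three days before the last dose.

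**2. Only the day missing.** Let D be the true day of the month, with D − 1 uniform on 0 to 29, and let g be the true gap in days from last dose to new therapy. The imputed start lies g − (D − 1) days after the last dose. For g up to 28:

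- Chance of falling on or before the last dose: (30 − g)/30.
- Mean post-dose time kept: g(g + 1)/60 days.
- Mean on-treatment time lost: (29 − g)(30 − g)/60 days.

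| g (days) | On or before last dose | Post-dose days kept | Post-dose window lost | On-treatment days lost |
|---|---|---|---|---|
| 14 | 16/30 = 53% | 14·15/60 = 3.5 | 1 − 3.5/14 = 75% | 15·16/60 = 4.0 |
| 21 | 9/30 = 30% | 21·22/60 = 7.7 | 1 − 7.7/21 = 63% | 8·9/60 = 1.2 |
| 28 | 2/30 = 7% | 28·29/60 = 13.5 | 1 − 13.5/28 = 52% | 1·2/60 = 0.03 |

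The harm fades with a longer gap. From g = 57 a missing day costs nothing, because 57 − 29 = 28.

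**3. Calendar count as a check.** First dose on each day of one year, last dose 42, 63 or 105 days later, Day 1 as the floor. The imputed start falls strictly before the last dose in 51%, 28% and 5% of cases at gaps of 14, 21 and 28 days, in line with step 2. As a share of the whole window from first dose, the mean loss at gaps of 7 to 28 days is 11% to 30%, depending on treatment length.

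**4. Month and day missing.** In the same count, for gaps of 42 down to 7 days, the imputed start precedes the last dose in 88% to 98% of cases. In 60% to 87%, 1 January precedes the first dose, so the override sets the start to Day 1 and nearly the whole window is emptied. The mean share of the whole window lost is 78% to 93%.

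**5. Override anchored at the last dose instead.** The zero-duration date is then the last dose itself. On-treatment AEs are safe, but whenever the override fires the entire post-dose window is lost. The post-dose losses in step 2 are unchanged, since they already count kept time as zero in those cases.

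**The case against.** Several points on the other side stand.

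- A reader might infer that the imputed date is checked against Day 1 and nothing else. Section 8.1 does not say so. The test is any negative duration, and Day 1 is an example for onset dates. It is the only anchor named, but a programmer could use the last dose. That choice would remove the on-treatment loss, but not the post-dose loss (step 5).
- A reader might infer that serious or dose-limiting events disappear. They do not. Deaths and serious AEs have their own bullets, and first-cycle DLTs are defined in Section 7.2.1 without any cut at new therapy. The Part 2 primary endpoint is response rate, and nothing here shows it affected.
- A reader might take the 52% to 75% as lost treatment time. These are shares of a post-dose window of at most 28 days. With only the day missing, the on-treatment loss averages 4 days or less at gaps of 14 days or more, against about 4 months of treatment (Section 2.1).
- Section 9.2.3 has no cut at new therapy. If its description is the one programmed, the loss does not arise.
- The tables count patients by worst grade, so a lost late event changes a count only if that patient had no earlier event of equal or worse grade.
- A reader might extend the point to time to progression, where Table 4 uses "Date of last objective tumor assessment prior to new anticancer treatment". That row measures new therapy from discontinuation of treatment. A start imputed before discontinuation gives a negative duration, and the override resets it. Time to progression is also not listed as an endpoint in Sections 2.4 or 7.1. This extension is marginal and the point does not rely on it.

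The direction of the error is not answered. Under either anchor, the Section 7.2.6 window can only shrink.

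**Conclusion.** The point holds in a limited form. Sections 8.1 and 7.2.6, applied together as written, bias the count of non-fatal, non-serious treatment-emergent AEs downwards, including those judged related. The loss is mainly post-dose. It is modest on treatment when only the day is missing, and can be large when only the year is known and Day 1 is the anchor.

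The figures rest on uniform dates, assumed gaps and assumed treatment lengths, and all are conditional on an incomplete new-therapy date. The SAP does not show how often that occurs, so the effect on the final tables cannot be estimated. The text also lets two programmers produce different tables, through the open anchor in Section 8.1 and the two descriptions in Sections 7.2.6 and 9.2.3. The documents do not support a claim that serious events, DLTs or the main efficacy results are distorted.

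**What to change.** Add to Section 8.1, for the treatment-emergent window only:

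- Set an incomplete start of new anticancer therapy to the latest date consistent with the known part: the last day of the known month, or 31 December if only the year is known. Cap it at death or last contact.
- Where the known part permits, the imputed start must fall after the last study dose. The condition matters: with therapy recorded as 'May' and a last dose on 10 June, an unconditional floor would give 11 June and contradict the known month.
- Do not exclude an AE with onset on or before the last study dose on the basis of an imputed new-therapy date alone.

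Then reconcile the treatment-emergent definitions in Sections 7.2.6 and 9.2.3.

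In the worked example the imputed start becomes 31 May, inside the 1 June limit, and no AE from the true window is lost. The cost is a few lines of text and a small programming change. A few AEs arising after the true start of new therapy may be counted as treatment-emergent (here, those of 27 to 31 May), which is the conservative direction for safety.

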### 8.2. Efficacy Analysis

Censoring rules for time-to-event endpoints are detailed in [Section 11.3 Appendix 3](#).

### **8.3. Pharmacokinetics**

#### **Concentrations below the limit of quantification**

In all data presentations (except listings), concentrations below the limit of quantification (BLQ) will be set to zero. (In listings BLQ values will be reported as “<LLQ”, where LLQ will be replaced with the value for the lower limit of quantification.).

#### **Deviations, missing concentrations and anomalous values**

In summary tables and plots of median profiles, statistics will be calculated with concentrations set to missing if one of the following cases is true:

1. A concentration has been reported as ND (ie, not done) or NS (ie, no sample),
2. A deviation in sampling time is of sufficient concern or a concentration has been flagged anomalous by the pharmacokineticist.

Note that summary statistics will not be presented at a particular time point if more than 50% of the data are missing.

#### **Pharmacokinetic parameters**

Actual PK sampling times will be used in the derivation of PK parameters.

If a PK parameter cannot be derived from a subject's concentration data, the parameter will be coded as NC (ie, not calculated). (Note that NC values will not be generated beyond the day that a subject discontinues).

In summary tables, statistics will not be presented for a particular treatment group if more than 50% of the data are NC. For statistical analyses, PK parameters coded as NC will also be set to missing.

If an individual subject has a known biased estimate of a PK parameter (due for example to an unexpected event such as vomiting before all the drug is absorbed in the body), this will be footnoted in summary tables and will not be included in the calculation of summary statistics or statistical analyses.

#### **QTc**

For the QTc analyses, no values will be imputed for missing data.

#### **Pharmacodynamic parameters**

Missing data for the pharmacodynamic parameters will be treated as such and no imputed values will be derived.

## **9. STATISTICAL METHODOLOGY AND STATISTICAL ANALYSES**

### **9.1. Statistical Methods**

No formal hypothesis testing will be performed in this exploratory study.

#### **Analyses of Time-to-Event Endpoints**

Time-to-event endpoints will be summarized using the Kaplan-Meier method and displayed graphically when appropriate. Median event times and 2-sided 95% confidence intervals for each time-to-event endpoint (Brookmeyer and Crowley, 1982) will be provided.

#### **Analyses of Binary Endpoint**

The rates of binary endpoints will be provided along with the corresponding 2-sided 95% confidence intervals using an exact method.

#### **Analyses of Continuous Data**

Descriptive statistics, such as the mean, standard deviation, coefficient of variation, median, minimum, and maximum values, will be provided for continuous endpoints.

### **9.2. Statistical Analyses**

#### **9.2.1. Primary Analysis**

Dose Limiting Toxicity (DLT) is the primary endpoint of the dose escalation component of the study, which will be summarized by dose level using the Per Protocol Analysis Set for patients in the dose escalation portion of the study. A listing of the DLTs will also be provided.

If necessary, a summary and listing of the DLT by malignancy may be provided using the Per Protocol Analysis Set for patients in the MTD expansion portion of the study.

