## **6.2. 'PER PROTOCOL' Analysis Set**

Part 2: the per protocol (PP) analysis sets includes all enrolled patients (for each indication) who receive at least one dose of study medication and who do not have major treatment deviations during first cycle.

Specifically: Patients with major treatment deviations in Cycle 1 are not evaluable for the RP2D assessment and therefore will not be included in the PP analysis. Major deviations include failure to satisfy major entry criteria (eg, confirmation of the target disease; signed informed consent) or use of other anticancer treatments during the active treatment and disease follow-up phases other than as defined/allowed in this protocol. At least one baseline and one post-baseline disease assessment are required for the PP analysis.

Modified PP analysis sets may be considered for additional analyses and would include patients enrolled either in Part 1 or in Part 2.

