## 6.8. Protocol Deviations

All deviations will be listed in the CSR. Major treatment deviations include, but are not limited to, less than 80% of the planned Cycle 1 PF-06647263 dose provided the reduction/omission is not due to treatment-related toxicity. Subjects with major Cycle 1 treatment deviations are not evaluable for MTD.

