### **7.2.2. MTD Definition**

The MTD would be any doses with true toxicity probabilities in the Equivalence Interval (EI) where the EI is defined as [20%-30%].

In practice, the MTD will be the highest dose associated with the occurrence of DLTs  $\leq 33\%$  (eg, 3/9 evaluable patients experience a DLT during the first treatment cycle).

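### The Part 1 primary DLT summary cites a Per Protocol set that the SAP defines only for Part 2, with a tumour-scan condition that does not belong to a Cycle 1 toxicity endpoint

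*SAP*

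**What the plan says.** SAP 2.4 makes first-cycle DLT the primary endpoint of Part 1. Section 9.2.1 says that it "will be summarized by dose level using the Per Protocol Analysis Set for patients in the dose escalation portion of the study", and adds a DLT listing for which it names no analysis set. For Part 2 it says: "If necessary, a summary and listing of the DLT by malignancy may be provided using the Per Protocol Analysis Set", there for the expansion patients.

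The PP set has one definition, in 6.2. It opens "Part 2: the per protocol (PP) analysis sets includes all enrolled patients (for each indication" and closes the bracket. It then requires at least one dose and no major treatment deviation in Cycle 1, and adds: "At least one baseline and one post-baseline disease assessment are required for the PP analysis". Part 1 is mentioned once in 6.2: "Modified PP analysis sets may be considered for additional analyses and would include patients enrolled either in Part 1 or in Part 2".

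Evaluability for the MTD is treated in 6.8: "Subjects with major Cycle 1 treatment deviations are not evaluable for MTD". The named example of such a deviation is receipt of under 80% of the intended Cycle 1 dose, "provided the reduction/omission is not due to treatment-related toxicity". The list is expressly open. Section 7.2.2 illustrates the MTD rule with "3/9 evaluable patients experience a DLT during the first treatment cycle".

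**The concern.** A first-cycle DLT is established from toxicity data; the definition in 7.2.1 involves no tumour assessment. A condition that a patient must have a post-baseline scan therefore has no bearing on whether that patient contributes information on DLT. It can also remove patients for reasons connected with the outcome: someone who stops early because of toxicity may never reach a scan.

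What is at stake is the denominator, and possibly the numerator, of the reported primary DLT rate. If the set is left to be settled at programming, the rate in the study report may rest on different patients from those counted as evaluable for the MTD. At cohort sizes of about nine, one patient changes the rate visibly.

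**Working it through.** **Step 1: the texts side by side.**

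| Feature | PP set (6.2) | MTD evaluability (6.8) |
|---|---|---|
| Part of the study | Labelled Part 2, per indication | No restriction to a part |
| Cycle 1 treatment deviation | Excludes | Excludes |
| Dose shortfall due to treatment-related toxicity | Not mentioned | Does not count as the named deviation |
| Entry-criteria failure, other anticancer treatment | Named as major deviations | Not named, but the list is open |
| Baseline and post-baseline disease assessment | Required | Not mentioned |

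**Step 2: Part 1.** There are two readings. If the Part 2 label in 6.2 is taken literally, 9.2.1 cites a set with no Part 1 definition. If 6.2 is borrowed for Part 1, the scan condition comes with it. The sentence on modified PP sets does not help: it is optional, concerns additional analyses rather than the primary one, and gives no criteria.

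**Step 3: Part 2.** No borrowing is needed. The optional summary and listing by malignancy use the PP set as defined, so a treated patient with a DLT but no post-baseline assessment is left out of both.

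**Step 4: what one unscanned patient does to the rate.** The SAP gives no figure to reproduce here, so this is illustration only. With x DLTs among n patients:

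- Dropping a DLT patient gives (x − 1)/(n − 1), a change of −(n − x)/[n(n − 1)].
- Dropping a patient without a DLT gives x/(n − 1), a change of +x/[n(n − 1)].
- The exact (Clopper-Pearson) 95% interval runs from the 2.5% quantile of Beta(x, n − x + 1) to the 97.5% quantile of Beta(x + 1, n − x). SAP 9.1 calls for an exact method for binary endpoints.

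Inputs: x = 3, n = 9 is the example in 7.2.2. For Part 2, n = 15 per indication is from 2.3; x = 4 is an assumption.

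| Case | Rate | Exact 95% CI | Change, percentage points |
|---|---|---|---|
| Part 1 example, all counted | 3/9 = 33.3% | 7.5 to 70.1 | |
| DLT patient dropped | 2/8 = 25.0% | 3.2 to 65.1 | −6/72 = −8.3 |
| Non-DLT patient dropped | 3/8 = 37.5% | 8.5 to 75.5 | +3/72 = +4.2 |
| Part 2, all counted | 4/15 = 26.7% | 7.8 to 55.1 | |
| DLT patient dropped | 3/14 = 21.4% | 4.7 to 50.8 | −11/210 = −5.2 |
| Non-DLT patient dropped | 4/14 = 28.6% | 8.4 to 58.1 | +4/210 = +1.9 |

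The Part 1 rows apply only if 6.2 is borrowed; the Part 2 rows apply to 6.2 as it stands. Either sign is possible.

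**Step 5: where a dropped DLT would still appear.** The Part 1 listing has no named set, so it may show the event. The Part 2 listing is on the PP set and would not. The Cycle 1 adverse event tables in 9.2.3 use the Safety Analysis Set; they would show the event by grade but not identify it as a DLT.

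**The case against.** The case for leaving the text alone runs as follows. The label in 6.2 confines the definition to Part 2, so nothing says that the scan condition reaches Part 1. A programmer could turn to 6.8, which has no such condition, and lose no DLT patient. The protocol, which is not shown, may define a Part 1 set. The scan sentence may have been meant for efficacy, since 9.2.2.1 uses the PP set for response and time-to-event endpoints and separately asks for baseline and post-baseline assessments. The Part 2 DLT summary is optional, and DLT is not the Part 2 primary endpoint. No hypothesis is tested.

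Much of this stands as a limit on severity. It shows that the Part 1 loss of patients is conditional, and that the undefined set is established for this SAP only. It does not remove the defect: 9.2.1 cites the PP set by name without pointing to 6.8 or to the protocol, the scan sentence is not restricted to efficacy, and in Part 2 it applies as written.

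Three stronger readings should be resisted:

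- A reader might infer that escalation decisions or the MTD could be wrong. The SAP does not say that either uses the PP set; 7.2.2 speaks of evaluable patients.
- A reader might infer a downward bias in the DLT rate. That needs unscanned patients to be mainly DLT patients, and the SAP gives neither those shares nor the scan timing.
- A reader might take 6.8 as the complete list of reasons for non-evaluability. It does not claim to be.

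**Conclusion.** The point holds as a defect in the specification of the primary analysis set, and it should be fixed. Section 9.2.1 cites, for the Part 1 primary endpoint, a set whose only definition in this SAP is for Part 2 and carries a scan condition unsuited to a Cycle 1 toxicity rate. The optional Part 2 DLT outputs are subject to that condition as written.

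The consequence is confined to the reported DLT rate and its agreement with the count of patients evaluable for the MTD. Its direction and size cannot be given. In the SAP's own example one patient moves the reported rate by −8.3 or +4.2 percentage points, assuming that 6.2 is applied to Part 1 and that one of the nine lacks a scan. The harm is limited further because the Part 1 listing may still show the event, although neither the Part 2 listing nor the adverse event tables would identify a dropped DLT.

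**What to change.** 1. In Section 6, define a DLT-evaluable set for Parts 1 and 2: treated patients without a major Cycle 1 treatment deviation under the 6.8 rule, with toxicity-driven reductions or omissions remaining evaluable and no disease-assessment condition.
2. State whether the other major deviations named in 6.2 (entry-criteria failure, non-permitted anticancer treatment) also exclude a patient from this set, consistently with the patients counted for the MTD. Because the list in 6.8 is open, the set is not fixed until this is written down.
3. In 9.2.1, cite this set for both DLT summaries, and name the set used for each listing.
4. In 6.2, limit the scan condition to efficacy analyses.

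The MTD rule in 7.2.2 is not touched. The cost is SAP wording: one new definition, changed citations in 9.2.1 and a limiting phrase in 6.2. No new data are needed. Item 2 needs a decision by the study team, checked against the protocol and best made before programming.
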